### **11.2 Adverse Event Recording / Reporting**

#### **11.2.1 Adverse Event/Effect Definition**

An AE is defined as any untoward medical occurrence in a patient or clinical investigation subject, temporally associated with the use of a medical device, whether or not considered related to the medical device and/or procedure. Therefore, any AE can be any unfavorable and unintended sign (including an abnormal laboratory finding), symptom, or disease (new or exacerbated) temporally associated with the use of the medical device and/or procedure.

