## 11.4 Serious Adverse Event

### 11.4.1 Definitions

SAEs are defined as those AEs which meet any of the following criteria:

1. Results in death
2. Led to serious deterioration in the health of the subject, that either resulted in
  - a life-threatening illness or injury, or
  - a permanent impairment of a body structure or a body function, or
  - in-patient or prolonged hospitalization, or
  - medical or surgical intervention to prevent life-threatening illness or injury or permanent impairment to a body structure or a body function.
3. Led to fetal distress, fetal death or a congenital abnormality or birth defect.

NOTE: Planned hospitalization for a pre-existing condition or a planned procedure, without serious deterioration in health, is not considered a SAE.

The following are not considered SAEs:

- Planned hospitalization.
- Anticipated day-to-day fluctuations of pre-existing condition(s) present and that do not worsen.

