### 1.1 Rationale for Amendment 1.0

The protocol original version 1.0 (dated 18 Feb 2014) was conducted and the device performance and safety data were summarized, including retrospective safety data for 2 hours following the apheresis procedure. Upon consideration of study results by the US Food and Drug Administration, regulators requested retrospective safety data not just for the 2 hours following the apheresis procedure, but also for the full 24 hours following the apheresis procedure.

This amendment was made to address regulatory agency feedback and to extend the duration of safety data collection following the apheresis procedure. With this amendment, safety data (eg, adverse events [AEs], blood product transfusions, and clinical laboratory results, as available) will be collected for the full 24-hour time period following the WBCD procedure, as requested by the US Food and Drug Administration. Under protocol version 1.0 (dated 18 Feb 2014), safety data were collected for the first 2 hours following apheresis; this amendment will collect safety data in the 22-hour time period from 2 hours postapheresis until 24 hours postapheresis.

This protocol amendment does not make changes to any of the following topics defined in the protocol original version (dated 18 Feb 2014): the study population, the definition of AEs and serious adverse events (SAEs), AE characterizations (eg, severity, action taken, relationship, outcome, SAE criteria), data analysis, or study management procedures.

This amendment does collect the following new information:

- Collection of AEs in the 22-hour time period from 2 hours postapheresis until 24 hours postapheresis
- Additional characterization of AE relationship to underlying disease or treatment for underlying disease (eg, chemotherapy)
- Reason for transfusion of blood products, if transfusions were administered in the 24-hour period postapheresis
- Postapheresis clinical laboratory results, as available

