#### **4. SAFETY ANALYSES**

The initial set of safety summary tables will remain as the core safety analysis and describe the safety profile from the start of the procedure through 2 hours post procedure. Additional adverse event tables will be added to summarize (cumulative) adverse events from the start of the procedure through 24 hours post procedure. These new summary tables will only include information from Sites 1 and 3 since 24 hour data are not available from Site 2.

The individual tables repeated for the 24 hour safety analysis can be found in the Table of Contents in Appendix 1.

An update was made to the definition of treatment emergent. In this retrospective study, it was originally assumed that all adverse events entered were treatment emergent. Given the updates to the adverse event data collection, subjects with multiple procedures may have events repeated across subsequent procedures. In cases where the onset date is clearly prior to the procedure (ie, onset date < procedure date), these events will not be considered treatment emergent.

While additional safety data will be collected with respect to laboratory data through 24 hours, no summarization is planned. All 24 hour lab data will be listed.

A summary table of patients receiving blood products transfused will be provided by product and timepoint.

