#### **5. GENERAL CONSIDERATIONS FOR DATA ANALYSIS**

Efforts will be made to compare data extracted from the Merge database to the original database. However, some changes are expected. There are new variables such as the use of blood warmers, toxicity grade of some pre-existing conditions, and relationship to underlying disease or treatment for underlying disease (adverse events). Sites were also given the opportunity to correct any information previously recorded in the original database that they find incorrect.

There will be additional updates to the procedure duration. In the original CRF, the procedure duration was captured rather than the procedure end time. In the new EDC, procedure start times, durations, and stop times are available for sites to confirm. The stop times entered in EDC are based on existing data on duration. Due to the potential for sites to modify the stop time (suggesting the original duration was incorrect), this re-analysis will use a derived duration rather than the original. The procedure stop time is critical for data capture as it is used for defining the 24 hour post procedure period.

Given the number of safety tables (including subsets), some summary tables may not have sufficient data. Thus, some tables may be omitted from the final analysis due to insufficient data.

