## **7. APPENDICES**

### **Appendix 1. Tables, Listings, and Figures**

## Appendix 1. Tables, Listings, and Figures

Table of Contents:

Table 14.1.1	Disposition	All Subjects and All Procedures
Table 14.1.2	Demographics and Baseline Characteristics	Safety Analysis Set
Table 14.2.1.1	Percent Decrease in WBC	Full Analysis Set
Figure 14.2.1.1	Percent Decrease in WBC	Full Analysis Set
Table 14.2.1.2	Percent Decrease in WBC	Per-Protocol Set
Figure 14.2.1.2	Percent Decrease in WBC	Per-Protocol Set
Table 14.2.2.1	Percent Processed WBC (CE1)	Full Analysis Set
Figure 14.2.2.1	Percent Processed WBC (CE1)	Full Analysis Set
Table 14.2.2.2	Percent Processed WBC (CE1)	Per-Protocol Set
Figure 14.2.2.2	Percent Processed WBC (CE1)	Per-Protocol Set
Table 14.2.3	WBCD Procedure Summary	Full Analysis Set
Table 14.3.2	Summary of HCT	Full Analysis Set
Table 14.3.1.1.1	Overview of Treatment Emergent Adverse Events	Safety Analysis Set – 2 Hour Monitoring
Table 14.3.1.1.2	Overview of Treatment Emergent Adverse Events	Safety Analysis Set – 24 Hour Monitoring
Table 14.3.1.2.1	Treatment Emergent Adverse Events by SOC and PT	Safety Analysis Set – 2 Hour Monitoring
Table 14.3.1.2.2	Treatment Emergent Adverse Events by SOC and PT	Safety Analysis Set – 24 Hour Monitoring
Table 14.3.1.3.1	Treatment Emergent Adverse Events by Severity	Safety Analysis Set – 2 Hour Monitoring
Table 14.3.1.3.2	Treatment Emergent Adverse Events by Severity	Safety Analysis Set – 24 Hour Monitoring
Table 14.3.1.4	Treatment Emergent Adverse Events Leading to Discontinuation of Study Procedures	Safety Analysis Set – 2 Hour Monitoring
Table 14.3.1.5.1	Serious Treatment Emergent Adverse Events by SOC and PT	Safety Analysis Set – 2 Hour Monitoring
Table 14.3.1.5.2	Serious Treatment Emergent Adverse Events by SOC and PT	Safety Analysis Set – 24 Hour Monitoring
Table 14.3.1.6.1	Treatment Emergent Adverse Events Related to Study Device	Safety Analysis Set – 2 Hour Monitoring
Table 14.3.1.6.2	Treatment Emergent Adverse Events Related to Study Device	Safety Analysis Set – 24 Hour Monitoring
Table 14.3.1.7.1	Treatment Emergent Adverse Events Related to Study Procedure	Safety Analysis Set – 2 Hour Monitoring
Table 14.3.1.7.2	Treatment Emergent Adverse Events Related to Study Procedure	Safety Analysis Set – 24 Hour Monitoring

Table 14.3.1.8.1	Treatment Emergent Adverse Events Related to Underlying Disease	Safety Analysis Set – 2 Hour Monitoring

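### The treatment-emergent rule uses onset date alone, so an event that began before a procedure and worsened during or after it can be missing from the AE tables for that procedure

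*SAP*

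**What the plan says.** SAP section 4 revises the treatment-emergent definition. It explains that in this retrospective study "it was originally assumed that all adverse events entered were treatment emergent", and that after the changes to AE collection "subjects with multiple procedures may have events repeated across subsequent procedures". The new rule is that where the "onset date is clearly prior to the procedure (ie, onset date < procedure date), these events will not be considered treatment emergent". The rule compares two calendar dates and contains no clause on severity or seriousness.

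Protocol section 11.2.1 defines an AE to include an unfavourable sign, "symptom, or disease (new or exacerbated) temporally associated with the use of the medical device and/or procedure". Section 1.1 of Amendment 1.0 lists "the definition of AEs and serious adverse events (SAEs), AE characterizations" among the topics it does not change. Protocol section 11.4.1 excludes from SAEs "Anticipated day-to-day fluctuations of pre-existing condition(s) present and that do not worsen".

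SAP Appendix 1 lists the AE summary tables, from "Overview of Treatment Emergent Adverse Events" (Table 14.3.1.1.1) to Table 14.3.1.9.2. Every one is titled as treatment emergent. SAP section 5 names "toxicity grade of some pre-existing conditions" among the variables new to the Merge database; the treatment-emergent rule does not use it.

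**The concern.** The protocol treats worsening as what makes a pre-existing condition count as an AE, and the SAP rule does not look at worsening. A record can therefore meet the protocol's AE definition and still be classed as not treatment emergent because of its onset date.

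The population makes this relevant. Protocol section 1.1.1 says hyperleukocytosis may cause respiratory failure, intracranial bleeding or acute renal failure, and section 10.2 records current symptoms before each procedure. Worsening of something already present is a plausible form in which procedural harm would show. The severity, serious, device-related and procedure-related tables are all among those restricted by the rule, and the 24-hour set was added because the regulator asked for safety data over that period.

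**Working it through.** No arithmetic is at issue beyond a count, so the check sets the texts side by side.

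**Step 1. Tables governed by the rule (SAP Appendix 1).**
- 2-hour tables: 14.3.1.1.1, 14.3.1.2.1, 14.3.1.3.1, 14.3.1.4, 14.3.1.5.1, 14.3.1.6.1, 14.3.1.7.1, 14.3.1.8.1 and 14.3.1.9.1 = 9.
- 24-hour tables: 14.3.1.1.2, 14.3.1.2.2, 14.3.1.3.2, 14.3.1.5.2, 14.3.1.6.2, 14.3.1.7.2, 14.3.1.8.2 and 14.3.1.9.2 = 8.
- Total: 9 + 8 = 17, and all 17 are titled treatment emergent. Listings 16.2.3.1 (adverse events) and 16.2.3.3 (serious adverse events) carry no such restriction in their titles.

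**Step 2. The rule applied to four kinds of record.**

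| Record | Onset before procedure date? | Result under the rule |
|---|---|---|
| Presenting condition entered as an AE with its true onset date; worsens in the window of procedure 1 | Yes | Excluded. There is no earlier procedure to count it under, so it enters no AE table |
| Event begins on day 1 within the window of procedure 1; repeated under procedure 2 on day 2 at a higher grade, onset still day 1 | Yes, for procedure 2 | The procedure 2 record is excluded. The procedure 1 record is tabulated, possibly at the lower grade |
| Same event repeated under procedure 2 at an unchanged grade | Yes, for procedure 2 | Excluded, as the rule intends |
| Worsening entered as a new AE with its own onset on or after the procedure date | No | Kept |

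**Step 3. Comparison with the protocol.** The first two rows describe exacerbations, which section 11.2.1 counts as AEs if temporally associated with the procedure. The third row is the double counting the SAP wants to remove. A date test cannot separate the second row from the third; only a comparison of grade or seriousness can.

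**Step 4. Which convention sites followed.** Amendment 1.0 section 2.4 collects start and end date and time and a severity for each AE. Neither document says whether a worsening is a new record with a new start or a repeat of the existing one. Rows 1 and 2 depend on the second convention, row 4 on the first. SAP section 4 expects repeats under later procedures and describes some with onset before the procedure date, so row 2 records are at least contemplated.

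**Step 5. Scale.** The number of such records cannot be obtained from the documents. Protocol section 8.1 targets at least 20 procedures, so at exactly 20 a single event would move a procedure-level rate by 1/20 = 5 percentage points. That is the weight of any one event in a study of this size. It is not an estimate of how many are lost.

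**The case against.** The strongest reply is that the loss depends on a recording convention the documents do not state. Section 11.2.1 makes the exacerbation itself an AE, and the protocol and amendment capture AEs occurring within a window, each with its own start time. A site could properly enter a worsening as an AE starting when it worsened, and the rule would keep it. Medical history also has its own CRF page, so a presenting condition need not appear as an AE with a pre-procedure onset. This stands, and it limits the point to records that keep their initial onset date.

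A reader might infer that worsened events vanish from the report altogether. The documents do not support that. An event that began within an earlier procedure's window is still tabulated under that procedure. At Sites 1 and 3, a worsening within 24 hours of that earlier procedure also falls inside its cumulative window. The two listings should show the events in any case, and in a small descriptive study listings can be read case by case. Listings do not, however, supply the rates or the severity and relatedness summaries.

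A reader might also infer that severe events suffer most. Nothing shows this, because the rule does not depend on grade.

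Preventing double counting is a legitimate aim, and a worsening exception does not undo it: unchanged repeats stay excluded.

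**Conclusion.** The point holds in a limited form. The SAP rule can remove AEs that the protocol defines as such from all 17 treatment-emergent tables for the affected procedure. A presenting condition that worsens then enters none of them. A carried-over event loses its record under the later procedure, and with it possibly the higher grade, a change to serious, or the relatedness judged at that procedure.

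This rests on two things: that at least some worsenings sit on records with the initial onset date, which the documents neither confirm nor exclude, and that the listings are unrestricted, which is inferred from their titles. The number affected is unknown. The direction is known: a rule that only excludes can only lower the tabulated counts. It should be corrected before the 24-hour tables are relied on, but it is not evidence that the reported rates are materially wrong.

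**What to change.** Amend SAP section 4 along these lines: an event with onset before the procedure date is not treatment emergent for that procedure unless its recorded grade increased, or it became serious, between the start of that procedure and the end of the 2-hour or 24-hour window being summarised.

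Three supporting statements are needed:
- For a repeated AE, compare its severity with the prior record; for a pre-existing condition, compare with the toxicity grade in Merge where one was collected.
- A worsening entered as a new AE has its own onset date and is judged on that date.
- Any prior-onset event with no baseline grade is flagged in Listing 16.2.3.1, so that readers can see what could not be classified.

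The cost is a short SAP amendment and a programming condition, with a few more events counted. The data are the real constraint. Amendment 1.0 lists a severity per AE, not serial grades, and a toxicity grade exists for only some pre-existing conditions. Some site queries will be needed. The procedures date from 2011 to 2013 and the amendment from 2016, so some queries may not be answerable; the flag covers those cases.

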#### **5. GENERAL CONSIDERATIONS FOR DATA ANALYSIS**

Efforts will be made to compare data extracted from the Merge database to the original database. However, some changes are expected. There are new variables such as the use of blood warmers, toxicity grade of some pre-existing conditions, and relationship to underlying disease or treatment for underlying disease (adverse events). Sites were also given the opportunity to correct any information previously recorded in the original database that they find incorrect.

There will be additional updates to the procedure duration. In the original CRF, the procedure duration was captured rather than the procedure end time. In the new EDC, procedure start times, durations, and stop times are available for sites to confirm. The stop times entered in EDC are based on existing data on duration. Due to the potential for sites to modify the stop time (suggesting the original duration was incorrect), this re-analysis will use a derived duration rather than the original. The procedure stop time is critical for data capture as it is used for defining the 24 hour post procedure period.

Given the number of safety tables (including subsets), some summary tables may not have sufficient data. Thus, some tables may be omitted from the final analysis due to insufficient data.

## **7. APPENDICES**

### **Appendix 1. Tables, Listings, and Figures**

## Appendix 1. Tables, Listings, and Figures

Table of Contents:

Table 14.1.1	Disposition	All Subjects and All Procedures
Table 14.1.2	Demographics and Baseline Characteristics	Safety Analysis Set
Table 14.2.1.1	Percent Decrease in WBC	Full Analysis Set
Figure 14.2.1.1	Percent Decrease in WBC	Full Analysis Set
Table 14.2.1.2	Percent Decrease in WBC	Per-Protocol Set
Figure 14.2.1.2	Percent Decrease in WBC	Per-Protocol Set
Table 14.2.2.1	Percent Processed WBC (CE1)	Full Analysis Set
Figure 14.2.2.1	Percent Processed WBC (CE1)	Full Analysis Set
Table 14.2.2.2	Percent Processed WBC (CE1)	Per-Protocol Set
Figure 14.2.2.2	Percent Processed WBC (CE1)	Per-Protocol Set
Table 14.2.3	WBCD Procedure Summary	Full Analysis Set
Table 14.3.2	Summary of HCT	Full Analysis Set
Table 14.3.1.1.1	Overview of Treatment Emergent Adverse Events	Safety Analysis Set – 2 Hour Monitoring
Table 14.3.1.1.2	Overview of Treatment Emergent Adverse Events	Safety Analysis Set – 24 Hour Monitoring
Table 14.3.1.2.1	Treatment Emergent Adverse Events by SOC and PT	Safety Analysis Set – 2 Hour Monitoring
Table 14.3.1.2.2	Treatment Emergent Adverse Events by SOC and PT	Safety Analysis Set – 24 Hour Monitoring
Table 14.3.1.3.1	Treatment Emergent Adverse Events by Severity	Safety Analysis Set – 2 Hour Monitoring
Table 14.3.1.3.2	Treatment Emergent Adverse Events by Severity	Safety Analysis Set – 24 Hour Monitoring
Table 14.3.1.4	Treatment Emergent Adverse Events Leading to Discontinuation of Study Procedures	Safety Analysis Set – 2 Hour Monitoring
Table 14.3.1.5.1	Serious Treatment Emergent Adverse Events by SOC and PT	Safety Analysis Set – 2 Hour Monitoring
Table 14.3.1.5.2	Serious Treatment Emergent Adverse Events by SOC and PT	Safety Analysis Set – 24 Hour Monitoring
Table 14.3.1.6.1	Treatment Emergent Adverse Events Related to Study Device	Safety Analysis Set – 2 Hour Monitoring
Table 14.3.1.6.2	Treatment Emergent Adverse Events Related to Study Device	Safety Analysis Set – 24 Hour Monitoring
Table 14.3.1.7.1	Treatment Emergent Adverse Events Related to Study Procedure	Safety Analysis Set – 2 Hour Monitoring
Table 14.3.1.7.2	Treatment Emergent Adverse Events Related to Study Procedure	Safety Analysis Set – 24 Hour Monitoring

Table 14.3.1.8.1	Treatment Emergent Adverse Events Related to Underlying Disease	Safety Analysis Set – 2 Hour Monitoring
Table 14.3.1.8.2	Treatment Emergent Adverse Events Related to Underlying Disease	Safety Analysis Set – 24 Hour Monitoring
Table 14.3.1.9.1	Treatment Emergent Adverse Events Related to Treatment of Underlying Disease	Safety Analysis Set – 2 Hour Monitoring
Table 14.3.1.9.2	Treatment Emergent Adverse Events Related to Treatment of Underlying Disease	Safety Analysis Set – 24 Hour Monitoring
Table 14.3.2	Summary of Blood Products Transfused	Safety Analysis Set

Listings:

Listing 16.2.1.1	Disposition	Safety Analysis Set
Listing 16.2.1.2	Demographics and Baseline Characteristics	Safety Analysis Set
Listing 16.2.1.3	Medical History	Safety Analysis Set
Listing 16.2.1.4	Prior and Concomitant Medication	Safety Analysis Set
Listing 16.2.1.5	Blood Products Transfused	Safety Analysis Set
Listing 16.2.1.6	Anticoagulants	Safety Analysis Set
Listing 16.2.1.7	Replacement Fluids	Safety Analysis Set
Listing 16.2.2.1	White Blood Cell Depletion	Full Analysis Set
Listing 16.2.2.2	White Blood Cells Processed	Full Analysis Set
Listing 16.2.2.3	Waste Bag CBC	Full Analysis Set
Listing 16.2.2.4.1	Pre/Post Procedure Lab Results	Full Analysis Set
Listing 16.2.2.4.2	Pre/Post Procedure Calcium Results	Full Analysis Set
Listing 16.2.2.4.3	Pre/Post Procedure Potassium Results	Full Analysis Set
Listing 16.2.2.4.4	Patients with Low Platelets	Full Analysis Set
Listing 16.2.3.1	Adverse Events	Safety Analysis Set
Listing 16.2.3.2	Adverse Events Leading to Discontinuation of Study Procedures	Safety Analysis Set
Listing 16.2.3.3	Serious Adverse Events	Safety Analysis Set
Listing 16.2.3.4	Vital Signs	Safety Analysis Set
